9.3.2 Analysis of Secondary Efficacy Endpoints

Key Secondary Endpoint

- Relative change from baseline in exercise duration during CPET at Week 24

Other Secondary Endpoints

- Absolute change from baseline in exercise duration during CPET at Week 24
- Absolute change from baseline in VO_2 max during cardiopulmonary exercise testing (CPET) at Week 24
- Absolute and relative change from baseline in oxygen consumption (VO_2) at anaerobic threshold (AT) (the point during exercise at which lactate starts to accumulate) at Week 24
- Absolute and relative change from baseline in functional VO_2 gain at Week 24
- Absolute and relative change from baseline in the slope of pulmonary ventilation (VE) versus carbon dioxide production (VCO_2) at Week 24
- Absolute change from baseline in percent predicted forced expiratory volume in 1 second (ppFEV₁) at Week 24
- Relative change from baseline in percent predicted forced expiratory volume in 1 second (ppFEV₁) at Week 24
- Absolute change from baseline in body mass index (BMI) at Week 24
- Relative change from baseline in body mass index (BMI) at week 24
- Absolute change from baseline in Cystic Fibrosis Questionnaire-Revised (CFQ-R) respiratory domain score at Week 24
- Absolute change from baseline in overall Patient Health Questionnaire (PHQ-8) and Generalized Anxiety Disorder (GAD-7) scores at Week 24
- Absolute change from baseline in total daily physical activity as determined by actigraphy at Week 24

- Relative change from baseline in total daily physical activity as determined by actigraphy at Week 24
- Absolute change from baseline in duration of sleep time during the night at Week 24
- Relative change from baseline in duration of sleep time during the night at Week 24
- Absolute change from baseline in time above sedentary duration at Week 24
- Relative change from baseline in time above sedentary duration at Week 24

9.3.2.1 Definition of Secondary Efficacy Endpoints

9.3.2.1.1 Definition of Key Secondary Efficacy Endpoints

Relative change from baseline in exercise duration during CPET at Week 24

Relative change from baseline in exercise duration measured in the unit of seconds during CPET at Week 24 is the key secondary efficacy endpoint, defined as exercise duration measured in the unit of seconds during CPET at Week 24 minus exercise duration measured in the unit of seconds during CPET at baseline, divided by exercise duration measured in the unit of seconds during CPET at baseline.

Exercise duration is defined as the time at the termination of CPET exercise minus the corresponding time when CPET starts for each CPET exercise.

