7 STUDY ENDPOINTS

7.1 Primary Endpoint

Percentage change from baseline in VO_{2max} during cardiopulmonary exercise testing (CPET) at Week 24

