7.2 Secondary Endpoints

Key Secondary Endpoint

- Change from baseline in exercise duration during CPET at Week 24

Other Secondary Endpoints

- Change from baseline in oxygen consumption (VO_2) at anaerobic threshold (AT) (the exercise intensity at which lactate starts to accumulate) at Week 24
- Change from baseline in functional VO_2 gain at Week 24
- Change from baseline in the pulmonary ventilation (VE) versus carbon dioxide production (VCO_2) slope at Week 24
- Change from baseline in percent predicted forced expiratory volume in 1 second (ppFEV₁) at Week 24
- Change from baseline in body mass index (BMI) at Week 24
 - Change from baseline in Cystic Fibrosis Questionnaire-Revised (CFQ-R) respiratory domain score at Week 24
 - Change from baseline in overall Patient Health Questionnaire (PHQ-8) and Generalized Anxiety Disorder (GAD-7) scores at Week 24
- Change from baseline in physical activity as determined by actigraphy at Week 24
- Change from baseline in duration of sleep time and change in sleep quality during the night at Week 24
- Safety and tolerability assessments based on adverse events (AEs), clinical laboratory values (serum chemistry and hematology), vital signs, and ophthalmologic examinations (for subjects under 18 years of age only).

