12.3.1 General Considerations

All individual subject data for the FAS will be presented in data listings.

Continuous variables will be summarized using the following descriptive summary statistics: the number of observations (n), mean, SD, median, minimum value (min), and maximum value (max).

Categorical data will be summarized using counts and percentages.

Baseline for a variable will, unless specifically stated otherwise, be defined as the most recent non-missing measurement (scheduled or unscheduled) collected before the initial administration of study drug. For actigraphy variables, baseline will be the data collected for 1 week during the Screening Period.

Change from baseline will be calculated as post-baseline value minus baseline value.

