12.3.3.2 Analysis of Secondary Efficacy Variables

Key Secondary Efficacy Endpoint:

The key secondary efficacy endpoint is the change from baseline in exercise duration during CPET at Week 24. The same analysis method as for the primary efficacy endpoint will be used, with change from baseline in exercise duration as the dependent variable. To control for multiplicity, the test for change in exercise duration will only be considered statistically significant if the 2-sided *P* value is 0.05 or less and the test for the primary endpoint also is statistically significant.

Other Secondary Efficacy Endpoints:

All other secondary efficacy endpoints will be analyzed in a similar fashion. No adjustment for multiplicity will be made for these endpoints. The other secondary endpoints are listed in Section 7.2.

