4 INTRODUCTION

This SAP describes the planned final analyses for the Study VX15-809-112 data and is based on the

- approved clinical study protocol (Version 1.0, dated 15 January 2016),
- approved electronic case report form (eCRF) (dated 13 January 2017).

Study VX15-809-112 is a Phase 4, Randomized, Double-Blind, Placebo-Controlled, Parallel-Design Study of the Effect of Lumacaftor/Ivacaftor Combination Therapy on Exercise Tolerance in Subjects Aged 12 Years and Older With Cystic Fibrosis, Homozygous for the *F508del-CFTR* Mutation.

This SAP (Methods) documents the planned final statistical analyses of efficacy and safety introduced in the study protocol of VX15-809-112, and describes the corresponding data presentations. It also documents additional efficacy and safety analyses not specified in the protocol, which will provide supportive information to the scientific understanding of the drug entity.

The [REDACTED] Biostatistics Department will perform the statistical analysis of the efficacy and safety data under the supervision of Vertex Biometrics Department; SAS (Version 9.2, or higher) will be used to generate all statistical outputs (tables, figures, listings, and datasets). The SAP will be finalized and approved prior to the final clinical data lock and treatment unblinding for the study.

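### The protocol's gated key secondary is absolute change in exercise duration; the SAP makes relative change key, gives no reason, and drops the gate

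*SAP*

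**What the plan says.** **Protocol.** The primary endpoint in Protocol 7.1 is explicitly relative: "Percentage change from baseline in VO_{2max} during cardiopulmonary exercise testing (CPET) at Week 24". The key secondary in Protocol 7.2 is not: "Change from baseline in exercise duration during CPET at Week 24". Protocol 12.3.1 defines the term: "Change from baseline will be calculated as post-baseline value minus baseline value". Protocol 12.3.3.2 reuses the primary's model "with change from baseline in exercise duration as the dependent variable" and adds a gate: "To control for multiplicity, the test for change in exercise duration will only be considered statistically significant if" its 2-sided P value is 0.05 or less and the primary is also significant. No other secondary endpoint has multiplicity control.

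**SAP.** SAP 4 names protocol Version 1.0 of 15 January 2016 as its basis. SAP 9.1 gives the protocol's difference formula the name absolute change and defines relative change separately, as a percentage of baseline. SAP 9.3.2.1.1 then states: "Relative change from baseline in exercise duration measured in the unit of seconds during CPET at Week 24 is the key secondary efficacy endpoint". SAP 6.1.2 and 9.3.2 agree, and both list absolute change in duration among the other secondary endpoints; SAP 9.3.2.1.2 defines it as an additional one. SAP 9.3.2.2.1, headed as the analysis of the key secondary endpoints (plural), models both scales. SAP 9.3.2.4 makes no multiplicity adjustment anywhere. SAP 3 records no modifications.

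**The concern.** Exercise duration is the only secondary endpoint for which the protocol allows a controlled significance claim. That claim belongs to the difference in seconds. The SAP gives the key-secondary label to the percentage change, moves the protocol's endpoint down the list, and does not say that it has done so. It also removes the rule that made the label matter.

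If the primary succeeds and the two scales fall on opposite sides of 0.05, the protocol points to one P value and the SAP to the other. The reader would then have no documented basis for saying which one counts.

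**Working it through.** **1. The passages side by side**

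| Place | Scale for exercise duration | Status |
|---|---|---|
| Protocol 7.2, 12.3.1, 12.3.3.2 | Difference from baseline | Key secondary, gated on the primary |
| SAP 6.1.2 and 9.3.2 | Relative | Key secondary |
| SAP 6.1.2 and 9.3.2 | Absolute | Other secondary |
| SAP 9.3.2.1.1 | Relative | Key secondary |
| SAP 9.3.2.1.2 | Absolute | Additional secondary |
| SAP 9.3.2.2.1 | Both | Under the key-secondary analysis heading |
| SAP 9.3.2.4 | Not scale-specific | No gate |

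The protocol never uses the word absolute here. The reading rests on its own definition of change and on the contrast with the wording of the primary. SAP 9.1 confirms it by giving the same formula the name absolute change. SAP 9.3.2.2.1 is the only place where the model for absolute change in duration appears, because SAP 9.3.2.2.2 does not list it.

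**2. The plan's own figure.** For VO2max (difference 7.5%, SD 10%, 2-sided 0.05, 80% power), a two-sample t-test needs 29 per arm. With 10% dropout, 29/0.9 = 32.2, which rounds up to the stated 33. Evaluable subjects are then 33 × 0.9 = 29.7, or about 30 per arm. The choice of duration scale does not affect this figure. Neither document sizes or powers exercise duration.

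**3. Why the scales can differ.** With baseline B and follow-up Y, absolute change is Y − B and relative change is 100 × (Y − B)/B. Take an assumed baseline mean of 600 s and SD of 150 s. A gain of 67 s is 100 × 67/450 = 14.9% one SD below the mean and 100 × 67/750 = 8.9% one SD above it. Relative change therefore gives more weight to subjects with short baselines.

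**4. How often the conclusion differs.** All inputs except the sample size are assumed. Each simulated trial has 30 subjects per arm and is analysed by single-visit ANCOVA on treatment and baseline duration, a simplification of the planned MMRM, at 2-sided p ≤ 0.05. With a change SD of 90 s, the standard error is about 90 × √(2/30) = 23.2 s. Effects of 67 s and 47 s are then 2.9 and 2.0 standard errors, giving power near 80% and 50%.

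Percentage of trials in which one scale is significant and the other is not (baseline mean 600 s, 60,000 trials per scenario):

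| Baseline SD | 67 s, additive | 67 s, proportional | 47 s, additive | 47 s, proportional |
|---|---|---|---|---|
| 90 s | 3.4 | 3.4 | 4.7 | 4.6 |
| 120 s | 5.2 | 4.4 | 7.1 | 6.3 |
| 150 s | 7.9 | 5.6 | 9.7 | 7.7 |
| 180 s, no lower limit | 13.5 | 7.2 | 14.4 | 9.2 |
| 180 s, baselines below 200 s redrawn | 8.2 | 6.7 | 10.5 | 9.0 |

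Additive and proportional state whether changes are generated in seconds or in proportion to baseline. For baseline SDs of 90 to 150 s, the two test statistics correlate at 0.94 to 0.99.

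A second set of assumptions used a baseline mean of 550 s, change SD of 60 s, additive effect of 40 s, baselines floored at 150 s, and 20,000 trials per scenario. Disagreement was 4.4%, 8.2% and 14.5% at baseline coefficients of variation of 15%, 25% and 35%. With no true effect, it was 1.2%, 2.3% and 3.5%.

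None of these rates is conditioned on a significant primary.

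**The case against.** **Both scales are analysed.** SAP 9.3.2.2.1 applies the same MMRM to both on the FAS, so the protocol's analysis is fully kept. This stands and limits the point to which result may be claimed as the key secondary. A reader might infer that the protocol's endpoint has been lost; it has not.

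**Without a gate the label is moot.** Under SAP 9.3.2.4 the SAP attaches no controlled claim to either scale. That is correct within the SAP, but the protocol's gate has not been amended. Dropping it is a second departure concerning the same test and does not resolve the first.

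**Change is a generic word.** Protocol 12.3.1 defines it, so this does not stand.

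**Relative change matches the primary's scale.** That may be a good reason, but the SAP does not give it. SAP 4 says only "It also documents additional efficacy and safety analyses not specified in the protocol", which does not describe replacing the key secondary.

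**Stronger readings.** A reader might infer inflated type I error. The documents do not say that success on either scale suffices, and under no effect each test alone rejected in 4.7% to 5.3% of the second set's trials. Accepting whichever scale succeeded would give 5.8% to 6.6%, but neither document proposes that. A reader might also infer a choice made with results in view. SAP 4 has the SAP finalised before data lock and unblinding, and nothing in the documents suggests otherwise. Nor is the SAP wholly consistent on relative change: its definitions name that scale alone, but SAP 9.3.2.2.1 puts both under the key heading.

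**Conclusion.** The mismatch is established from the text and needs no simulation. The protocol's gated key secondary is absolute change; the SAP names relative change, classes absolute change as other or additional, blurs the distinction in its analysis section, gives no reason, and omits the gate.

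The practical effect is modest. The primary analysis is untouched, both results will exist, and the scales usually agree. The figure of roughly 3% to 15% disagreement is an illustration for trials with a true effect. It depends on assumed means, SDs and effects, on a single-visit model, and at the upper end on wide baseline variation and how very low baselines are handled. It is not an estimate for this trial. The point should be corrected before unblinding because the documents currently do not settle which P value supports the key secondary claim.

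**What to change.** Before unblinding:

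- In SAP 6.1.2, 9.3.2, 9.3.2.1.1 and 9.3.2.1.2, make absolute change in exercise duration, in seconds, the single key secondary endpoint, as in the protocol, with relative change as supportive.
- Retitle SAP 9.3.2.2.1 so that it shows which scale is key and which is supportive.
- Edit SAP 9.3.2.4 to carry the gate in Protocol 12.3.3.2 for that one endpoint, with no adjustment for the remaining secondaries.

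This is text in six SAP sections. Both scales are already derived and modelled, so no new data or programming are needed.

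If the sponsor prefers relative change, it should amend the protocol instead and record a dated reason in the SAP. SAP 9.3.2.2.1 and 9.3.2.4 would still need the edits above, applied to relative change. This route costs more: Protocol 13.2.3 requires investigator and sponsor approval and submission to the required authorities, plus prior IRB/IEC notification for changes that significantly affect scientific quality.

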9.3.2.1.2 Definition of Additional Secondary Efficacy Endpoints

Absolute change from baseline in exercise duration during CPET at Week 24

Defined as exercise duration measured in the unit of seconds during CPET at Week 24 minus exercise duration measured in the unit of seconds during CPET at baseline

Absolute change from baseline in VO_2 max (mL/kg/min) during cardiopulmonary exercise testing (CPET) at Week 24

Defined as $VO_2\text{max}$ (mL/kg/min) during cardiopulmonary exercise testing (CPET) at Week 24 minus $VO_2\text{max}$ (mL/kg/min) during cardiopulmonary exercise testing (CPET) at baseline

Absolute change from baseline in oxygen consumption (VO_2) (mL/min) at anaerobic threshold (AT) (the point during exercise at which lactate starts to accumulate) at Week 24

Defined as oxygen consumption (VO_2) (mL/min) at AT at Week 24 minus oxygen consumption (VO_2) (mL/min) at AT at baseline.

Relative change from baseline in oxygen consumption (VO_2) (mL/min) at anaerobic threshold (AT) (the point during exercise at which lactate starts to accumulate) at Week 24

Defined as oxygen consumption (VO_2) (mL/min) at AT at Week 24 minus oxygen consumption (VO_2) (mL/min) at AT at baseline, divided by oxygen consumption (VO_2) (mL/min) at AT at baseline

Before reviewing the results for VO_2 at the time that AT occurred, it must first be determined if the appropriate number of overreaders input this value into the eCRF. There are separate eCRF entries for the time at AT and the actual VO_2 value at the time of AT. However, each of these fields should have the identical number of entries, either 2 or 3. If they do not, no further evaluation of these parameters should be carried out, and Vertex must be notified. If they do, please proceed.

The time of AT is reported in the eCRF by either 2 or 3 independent overreaders. The final, averaged time at AT will be determined following the guidelines:

- If the time at AT results is available from two overreaders, the absolute difference between these results (in seconds) will be divided by the lower of the two results (in seconds) to determine if the readings are within 5% ($\leq 5\%$) of each other. If they are, the average value of the two readings will be used as the final time at AT. If the results are not within 5% of each other, no further evaluation of this parameter should be carried out, and Vertex must be notified.
- If time at AT results is available from 3 overreaders, the absolute difference between the highest and lowest of the 3 results (in seconds) will be divided by the lowest of the results (in seconds) to determine if these readings are within 7% ($\leq 7\%$) of each other. If they are, the average value of all three readings will be used as the final time at AT. If their results are not within 7% of each other, no further evaluation of this parameter should be carried out, and Vertex must be notified.

Once it has been confirmed that the appropriate number of overreaders have input their values, the average of these 2 or 3 VO_2 values in the eCRF will be reported as the final VO_2 at the time of AT.

Absolute change from baseline in functional VO₂ gain at Week 24

Defined as functional VO₂ gain at Week 24 minus functional VO₂ gain at baseline.

Relative change from baseline in functional VO₂ gain at Week 24

Defined as functional VO₂ gain at Week 24 minus functional VO₂ gain at baseline, divided by functional VO₂ gain at baseline.

Functional VO₂ gain is calculated as $\Delta \text{VO}_2 / \text{Max Watts}$.

This data is derived from the 20-second averaged CPET spreadsheets.

- $\Delta \text{VO}_2 = \text{Final VO}_2 - \text{Rest VO}_2$
 - Final VO₂ (ml/min) is the mean of the last 3 available values of VO₂ at the end of exercise
 - Rest VO₂ (ml/min) is the mean of the last 3 available values of VO₂ immediately before the start of exercise
- Maximum Watts achieved during exercise can be found in the WR, Work, or Watts column on the 20-sec averaged CPET spreadsheets.

If VO₂ reported in L/min, this will need to be converted to mL/min before applying the formulas above (1L=1000mL).

Absolute change from baseline in the slope of pulmonary ventilation (VE, L/min) versus carbon dioxide production (VCO₂, L/min) at Week 24

Defined as the slope of pulmonary ventilation (VE, L/min) versus carbon dioxide production (VCO₂, L/min) at Week 24 minus the slope of pulmonary ventilation (VE, L/min) versus carbon dioxide production (VCO₂, L/min) at baseline

Relative change from baseline in the slope of pulmonary ventilation (VE, L/min) versus carbon dioxide production (VCO₂, L/min) at Week 24

Defined as the slope of pulmonary ventilation (VE, L/min) versus carbon dioxide production (VCO₂, L/min) at Week 24 minus the slope of pulmonary ventilation (VE, L/min) versus carbon dioxide production (VCO₂, L/min) at baseline, divided by the slope of pulmonary ventilation (VE, L/min) versus carbon dioxide production (VCO₂, L/min) at baseline

This data is derived from the breath-by-breath CPET spreadsheets.

VE and VCO₂ data will be measured from the beginning to the end of exercise during each corresponding CPET session.

A linear regression model using pulmonary ventilation (VE, L/min) as the dependent variable and carbon dioxide production (VCO₂, L/min) as the covariate without an intercept will be used to derive the slope estimate from the breath by breath data.

Absolute change from baseline in percent predicted forced expiratory volume in 1 second (ppFEV₁) at Week 24

Defined as percent predicted forced expiratory volume in 1 second (ppFEV₁) at Week 24 minus percent predicted forced expiratory volume in 1 second (ppFEV₁) at baseline (Please see appendix D for the definition of ppFEV₁)

Relative change from baseline in percent predicted forced expiratory volume in 1 second (ppFEV₁) at Week 24

Defined as percent predicted forced expiratory volume in 1 second (ppFEV₁) at Week 24 minus percent predicted forced expiratory volume in 1 second (ppFEV₁) at baseline, divided by percent predicted forced expiratory volume in 1 second (ppFEV₁) at baseline (Please see appendix D for the definition of ppFEV₁)

Absolute change from baseline in body mass index (BMI) raw score at Week 24

Defined as body mass index (BMI) raw score at Week 24 minus body mass index (BMI) raw score at baseline

Relative change from baseline in body mass index (BMI) raw score at Week 24

Defined as body mass index (BMI) raw score at Week 24 minus body mass index (BMI) raw score at baseline, divided by body mass index (BMI) raw score at baseline

BMI will be calculated as the following:

$$\text{BMI} = \text{Weight (kg)} / (\text{height (m)}^2)$$

Absolute change from baseline in Cystic Fibrosis Questionnaire-Revised (CFQ-R) respiratory domain score at Week 24

Defined as Cystic Fibrosis Questionnaire-Revised (CFQ-R) respiratory domain score at Week 24 minus Cystic Fibrosis Questionnaire-Revised (CFQ-R) respiratory domain score at baseline

The CFQ-R^{2,3,4} is a validated CF-specific instrument that measures quality-of-life domains. There are three different versions of CFQ-R forms in this study:

- CFQ-R for Children Ages 12 and 13 has a total of 35 questions to form 8 domains. All questions are scored 1, 2, 3, or 4.
- CFQ-R for Adolescents and Adults (subjects 14 years and older) has a total of 50 questions to form 12 domains. Question 43 is scored 1, 2, 3, 4, or 5 and is not used in calculating any domains; all the other 49 questions are scored 1, 2, 3, or 4.
- CFQ-R for Parents/Caregivers (subjects 13 years and younger) has a total of 44 questions to form 11 domains. Question 37 is scored 1, 2, 3, 4, or 5 and is not used in calculating any domains; all the other 43 questions are scored 1, 2, 3, or 4.

For all three CFQ-R versions, to calculate the score for each domain, the response scores on the negatively phrased questions are reversed (reversed scores = 5 – response scores) so that 1 always represents the worst condition and 4 always represents the best condition. In each domain, in cases where individual questions were skipped, the missing scores are imputed with the mean score of the non-missing questions for that domain rounded to the nearest integer.

The scaled score for each domain ranges from 0 (worst condition) to 100 (best condition) and is calculated as follows:

$$\text{Scaled score for a domain} = 100 \times (\text{mean(scores of all questions in that domain)} - 1) / 3$$

The scaled score for a specific domain will not be calculated if more than half of the questions in the domain have missing scores.

Table 9-2, Table 9-3, and Table 9-4 provide the questions included in each domain, the questions with the reversed scores, as well as the maximum number of missing questions for the CFQ-R for Children Ages 12 and 13, the CFQ-R for Adolescents and Adults, and the CFQ-R for Parents/Caregivers respectively. [REDACTED]

Table 9-2 CFQ-R for Children Ages 12 and 13

Domain	Questions		Reversed questions	Maximum number of missing questions
	Total	Individual		
Physical	6	1, 2, 3, 4, 5, 6	1, 2, 3, 4, 5	3
Emotion	8	7, 8, 9, 10, 11, 12, 13, 14	14	4
Social	7	20, 21, 22, 23, 24, 25, 26	20, 22, 24, 26	3
Body	3	27, 28, 29	-	1
Eat	3	15, 17, 19	19	1
Treatment burden	3	16, 18, 30	18	1
Respiration	4	31, 32, 33, 34	-	2
Digestion	1	35	-	0

Table 9-3 CFQ-R for Adolescents and Adults (subjects 14 years and older)

Domain	Questions		Reversed questions	Maximum number of missing questions
	Total	Individual		
Physical	8	1, 2, 3, 4, 5, 13, 19, 20	13	4
Role	4	35, 36, 37, 38	35	2
Vitality	4	6, 9, 10, 11	6, 10	2
Emotion	5	7, 8, 12, 31, 33	-	2
Social	6	22, 23, 27, 28, 29, 30	23, 28, 30	3
Body	3	24, 25, 26	-	1
Eat	3	14, 21, 50	-	1

Table 9-3 CFQ-R for Adolescents and Adults (subjects 14 years and older)

Domain	Questions		Reversed questions	Maximum number of missing questions
	Total	Individual		
Treatment burden	3	15, 16, 17	15, 17	1
Health perceptions	3	18, 32, 34	18, 32, 34	1
Weight	1	39	-	0
Respiration*	6	40, 41, 42, 44, 45, 46	43	3
Digestion	3	47, 48, 49	-	1

*: Question 43 not used to calculate a domain.

Table 9-4 CFQ-R for Parents/Caregivers (subjects 13 years and younger)

Domain	Questions		Reversed questions	Maximum number of missing questions
	Total	Individual		
Physical	9	1, 2, 3, 4, 5, 13, 14, 15, 16	15	4
Vitality	5	8, 9, 10, 11, 12	10, 12	2
Emotion	5	6, 7, 23, 25, 26	6	2
School	3	27, 28, 29	28	1
Body	3	19, 20, 21	-	1
Eat	2	17, 44	-	0
Treatment burden	3	18, 30, 31	31	1
Health perceptions	3	22, 24, 32	22, 24, 32	1
Weight	1	33	-	0
Respiration*	6	34, 35, 36, 38, 39, 40	37	3
Digestion	3	41, 42, 43	-	1

*: Question 37 not used to calculate a domain.

The absolute change from baseline in the respiratory domain of the CFQ-R (Pooled 'Children Ages 12 and 13' Version and 'Adolescents and Adults' Version) at Week 24 is one of the secondary endpoints.

Absolute change from baseline in overall Patient Health Questionnaire (PHQ-8) and Generalized Anxiety Disorder (GAD-7) scores at Week 24

Defined as overall Patient Health Questionnaire (PHQ-8) and Generalized Anxiety Disorder (GAD-7) scores at Week 24 minus overall Patient Health Questionnaire (PHQ-8) and Generalized Anxiety Disorder (GAD-7) scores at baseline, correspondingly

Both GAD-7 and PHQ-8 will be summarized by proportion of patients in each severity category at both baseline and Week 24. The detailed information with regard to these two scores and the severity category is indicated below.

PHQ-8 Depression Severity. This is calculated by assigning scores of 0, 1, 2, and 3, to the response categories of —not at all, —several days, —more than half the days, and —nearly every day, respectively. PHQ-8 total score for the eight items ranges from 0 to 24. Scores of 5, 10, 15, and 20 represent cutpoint for mild, moderate, moderately severe and severe depression, respectively. Sensitivity to change has also been confirmed.

GAD-7 Anxiety Severity. This is calculated by assigning scores of 0, 1, 2, and 3, to the response categories of —not at all, —several days, —more than half the days, and —nearly every day, respectively. GAD-7 total score for the seven items ranges from 0 to 21. Scores of 5, 10, and 15 represent cutpoint for mild, moderate, and severe anxiety, respectively. Though designed primarily as a screening and severity measure for generalized anxiety disorder, the GAD-7 also has moderately good operating characteristics for three other common anxiety disorders – panic disorder, social anxiety disorder, and post-traumatic stress disorder. When screening for anxiety disorders, a recommended cutpoint for further evaluation is a score of 10 or greater.

██
██

Absolute change from baseline in physical activity as determined by actigraphy at Week 24

Defined as total activity count at Week 24 minus total activity count at baseline. Baseline is defined as the daily mean of data obtained in the 7 days prior to Day 1 (Day -7 through Day -1). Week 24 is defined as the mean of data obtained in the calendar week prior to Week 24.

Relative change from baseline in physical activity as determined by actigraphy at Week 24

Defined as total activity count at Week 24 minus total activity count at baseline, divided by total activity count at baseline. Baseline is defined as the daily mean of data obtained in the 7 days prior to Day 1 (Day -7 through Day -1). Week 24 is defined as the mean of data obtained in the calendar week prior to Week 24 visit.

Absolute change from baseline in duration of sleep time during the night at Week 24

Defined as average duration of sleep time at Week 24 minus average duration of sleep time at baseline. Baseline is defined as the daily mean of data obtained in the 7 days prior to Day 1 (Day -7 through Day -1).; week 24 is defined as the mean of data obtained in the calendar week prior to Week 24 visit.

Relative change from baseline in duration of sleep time during the night at Week 24

Defined as average duration of sleep time at Week 24 minus average duration of sleep time at baseline, divided by average duration of sleep time at baseline. Baseline is defined as the

daily mean of data obtained in the 7 days prior to Day 1 (Day -7 through Day -1).; week 24 is defined as the mean of data obtained in the calendar week prior to Week 24 visit.

Absolute change from baseline in time above sedentary duration at Week 24

Defined as average time above sedentary duration at Week 24 minus average time above sedentary duration at baseline. Baseline is defined as the daily mean of data obtained in the 7 days prior to Day 1 (Day -7 through Day -1).; week 24 is defined as the mean of data obtained in the calendar week prior to Week 24 visit.

Relative change from baseline in time above sedentary duration at Week 24

Defined as average time above sedentary duration at Week 24 minus average time above sedentary duration at baseline, divided by average time above sedentary duration at baseline. Baseline is defined as the daily mean of data obtained in the 7 days prior to Day 1 (Day -7 through Day -1).; week 24 is defined as the mean of data obtained in the calendar week prior to Week 24 visit.

The time unit for duration of sleep and time above sedentary duration will be in hours.

